7 SUBGROUP ANALYSES

- 1) A planned subgroup analysis will be conducted to test the effect of cognitive impairment (MoCA positive) on delirium (CAM positive) at 6 months only. This analysis should be considered exploratory. A subgroup effect will be investigated through fitting an interaction term for cognitive impairment and randomised group into a generalised linear mixed model with delirium at 6 months as the outcome. The model will include the interaction term for cognitive impairment and randomised group, gender, known cognitive decline, and baseline delirium as fixed effects, and centre as a random effect. The results for the subgroup analysis will be reported in a forest plot, along with the overall intervention effect. In addition to the effect size and 95% CI for the intervention effect in each level of the subgroup, the p value for the interaction term will be reported.

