2.1 OUTCOMES MEASURES

Outcomes are measured at baseline, 6 months and 12 months (excluding delirium which is measured at 3 days, 5 days and 1 month) after randomisation. Data will be entered directly onto CRFs and e-CRFs

See Appendix II for a table of outcome assessment schedule.

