2.1.2 SECONDARY OUTCOMES FOR THE PRIMARY OBJECTIVE

The secondary outcomes for the primary objective are: presence of delirium, mortality, new long-term residential care, cognitive impairment, activities of daily living, quality of life, quality adjusted survival, length of stay in hospital, readmission or transfer to hospital, resource use (health and social care and informal care), and costs and cost-effectiveness, see Appendix III for questionnaire scoring.

1) Incident and Persistent of Delirium (CAM) at baseline, 3 days, 5 days, and 1 month

The Confusion Assessment Method (CAM) diagnostic algorithm [1] is used to derive a variable for delirium, and is assessed at baseline, 3 days, 5 days and 1 month follow-up. CAM is split into 4 features (acute onset and fluctuating course, inattention, disorganized thinking, and altered level of consciousness).

Feature 1 (acute onset and fluctuating course) is present if there is evidence of an acute change in mental status from the patient's baseline (variable *cam1*) **AND** the behaviour fluctuated during the interview (variable *cam2b*). Feature 2 (inattention) is present if the patient had difficulty focusing attention during the interview in either mild or marked form (variable *cam2a*). Feature 3 (disorganized thinking) is present if the patient's thinking is disorganised or incoherent (variable *cam3*). Feature 4 (altered level of consciousness) is present if the patient's level of consciousness is anything other than alert (or uncertain) (variable *cam4*).

A diagnosis of delirium will be coded as a binary variable (0 = absent, 1 = present) and is present if the patient is positive for a presence of acute onset and fluctuating discourse (feature 1) **AND** positive for inattention (feature 2) **AND EITHER** disorganised thinking (feature 3) **OR** altered level of consciousness (feature 4).

If 'not applicable' is answered it shall be treated as 'no', and delirium will be calculated for each patient unless all the items from these sections are missing, in this case the delirium score will be coded as missing.

2) Mortality at 3 days, 5 days, 1 month, 6 months and 12 months

Patient mortality status is collected at 3 days, 5 days, 1 month, 6 months and 12 months after randomisation on the respective follow-up CRFs, date and details of a patient's death is collected on

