5 SECONDARY ANALYSIS

5.1 SECONDARY OUTCOMES

1) 'Living at home' at 12 months

The 'living at home' at 12 months outcome will be analysed separately from the 6 months analysis (since the main analysis shall be carried out after 6 months but before the 12 months follow-up data has been collected) and will not be reported in the main report, instead it will be reported in a separate statistical analysis report. The data will be analysed using a generalised linear mixed models as described in section 4.1, with 'living at home' at 12 months as the outcome. The intervention effect with 95% confidence interval and p-value will be reported.

2) Presence of delirium at 3 days, 5 days, and 1 month (CAM)

Presence of delirium is assessed at baseline, 3 days, 5 days, and at 1 month, by the Confusion Assessment Method (CAM) and is a binary variable. A generalised linear mixed model will be used similar to the primary analysis (section 4.1) with presence of delirium at 3 days and 5 days, and

presence of delirium at 1 month as the dependent variable. The model will include intervention arm, baseline CAM, stratification factors (gender and known cognitive decline (IQCODE)) as fixed effects; and centre as a random effect. The model will also include a random interception for each patient. The model will include an interaction between time and randomised group as a fixed effect. The adjusted relative risk between randomised groups with 95% CI and p-value for presence of delirium at 3 days, 5 days, and at 1 month will be estimated from the model.

3) Mortality at 6 months and 12 months

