13 APPENDICES

Appendix I. Schedule of study procedures

Procedures	Visit					
	Baseline	3 days	5 days	1 month	6 months	12 months
Informed consent	X					
Eligibility assessment	X	X	X		X	X
Randomisation	X					
Demographics	X					
Medical history	X					
Physical examination (where judged clinically appropriate)	X					
Trial specific questionnaires	X ¹²³	X ²	X ²	X ²	X ³	
Health resource questionnaire	X				X	
Patient feedback questionnaire				X		
Adverse event assessment		X	X		X	X

¹ Short form of the informant questionnaire on cognitive decline in the elderly measured at baseline only

² Confusion assessment method measured at baseline, 3 days, 5 days, and 1 month only.

³ Barthel index of activities of daily living, Charlson comorbidity index, Montreal cognitive assessment and EQ-5D-5L measured at baseline and 6 months only.

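### The SAP's one planned subgroup analysis (exploratory) takes CAM delirium at 6 months as its outcome, but CAM is not scheduled after 1 month, so it cannot be run as written

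*SAP*

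**What the plan says.** Section 7 contains one item. Its aim is to "test the effect of cognitive impairment (MoCA positive) on delirium (CAM positive) at 6 months only", and its method is "fitting an interaction term for cognitive impairment and randomised group into a generalised linear mixed model with delirium at 6 months as the outcome". The 6-month time point is therefore given twice. The section calls the analysis exploratory. It promises a forest plot with the effect in each subgroup level, the overall intervention effect and an interaction p-value.

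The rest of the SAP gives a different schedule for delirium:

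- Section 2.1 sets outcome measurement at baseline, 6 and 12 months, "excluding delirium which is measured at 3 days, 5 days and 1 month".
- Section 2.1.2, item 1, says that the CAM-based delirium variable "is assessed at baseline, 3 days, 5 days and 1 month follow-up".
- Section 5.1, item 2: "Presence of delirium is assessed at baseline, 3 days, 5 days, and at 1 month, by the Confusion Assessment Method (CAM").
- Section 8, item 2, repeats the same four times and adds a clinical diagnosis of delirium, described at baseline only.
- Appendix I, footnote 2: "Confusion assessment method measured at baseline, 3 days, 5 days, and 1 month only".
- Appendix II has four marks in the CAM row and none under 6 or 12 months.

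MoCA, which defines the subgroup, is taken at baseline and at 6 months (section 2.1.2, item 4; Appendices I and II). Section 7 does not say which of the two is meant.

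**The concern.** An analysis whose outcome is not collected has to be changed or dropped. If that happens after outcome data by arm have been seen, the delirium time point and the subgroup definition become choices made with the results in view, yet the analysis would still carry the label of a planned one. The SAP states no safeguard that would catch this. Section 2.4 describes no blinding of the analysts, section 4.4 makes no multiplicity adjustment, and the minimum validation list in section 10 does not include the subgroup analysis.

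The subgroup variable is also under-defined. Its time point is missing and its direction is unclear, so correcting the outcome time alone would not fully fix the analysis.

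**Working it through.** No sample size, power or alpha figure bears on this point. The check compares section 7 with each statement of the schedule.

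**1. Is delirium scheduled at 6 months?**

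| Place in SAP | Delirium/CAM times | 6 months? |
|---|---|---|
| 2.1 | 3 days, 5 days, 1 month; excepted from the 6- and 12-month rule | No |
| 2.1.2, item 1 | baseline, 3 days, 5 days, 1 month | No |
| 5.1, item 2 | baseline, 3 days, 5 days, 1 month | No |
| 8, item 2 (CAM) | baseline, 3 days, 5 days, 1 month | No |
| 8, item 2 (clinical diagnosis) | baseline | No |
| Appendix I, footnote 2 | the same four, with the word *only* | No |
| Appendix II | four marks | No |
| **7** | **6 months** | **Yes** |

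Scheduled CAM time points: 4. Scheduled CAM assessments at 6 months: 0. Appendix I agrees from another direction: the 6-month mark for trial questionnaires carries only footnote 3 (Barthel, Charlson, MoCA, EQ-5D-5L). Section 11, which lists changes from the published protocol, mentions no added 6-month CAM.

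**2. Does the comparison estimate exist?** The forest plot is to show the overall intervention effect. Section 5.1, item 2, estimates the delirium effect at 3 days, 5 days and 1 month, so the SAP produces no overall delirium effect at 6 months either.

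**3. How much is left open?** There are three post-baseline CAM visits and two MoCA times, so 3 × 2 = 6 single-time-point versions could be fitted, before counting repeated-measures versions.

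**4. Which way does MoCA positive point?** Section 2.1.2, item 4, codes the variable named cognitive impairment as 0 for a score below 26 and 1 for 26 or more (cut-off 18 for the shortened version). A score of 26 or more is the normal range, so the value 1 means not impaired. Section 7 uses MoCA positive to mean cognitive impairment. Reversing a binary subgroup variable leaves the interaction p-value unchanged, but it swaps the labels on the two subgroup effects in the forest plot.

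**The case against.** The strongest reply is that little depends on this analysis. It is labelled exploratory and feeds no primary or secondary estimate. The delirium comparison between arms is specified separately, at visits where CAM is scheduled. A model with no outcome data also fails visibly; it cannot quietly give a wrong number. All of this stands, and it limits the weight of the point. It does not make the analysis runnable.

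A reader might infer more than the SAP supports:

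- *That the analysis will be rebuilt after the data are seen.* This is a risk, not a certainty. The SAP has a version history and a section for changes, so it can be corrected in time.
- *That the subgroup is defined by 6-month MoCA, and so by a post-randomisation measure in survivors.* Section 7 attaches 6 months to delirium, not to MoCA, and the one MoCA covariate specified elsewhere (section 5.1, item 5) is the baseline score. Only the omission of the time point is established.
- *That the model wrongly leaves out main effects.* Section 7 lists the interaction without them. However, section 5.1, items 2 and 4, likewise list a time-by-arm interaction without time, and the promised effect in each subgroup level ordinarily implies main effects. This is drafting shorthand that needs clarifying, not a separate error.
- *That 1-month CAM data are already in hand.* The SAP shows that the visit is scheduled. It gives no collection status or completeness.

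**Conclusion.** The contradiction is real and lies wholly within the SAP. Section 7 names a 6-month delirium outcome twice, and every other statement of the delirium schedule ends at 1 month. As written, the analysis has no scheduled outcome data and cannot be run. It is the only subgroup analysis planned, but it is exploratory, and the primary and secondary results do not depend on it. This is a should-fix point.

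The conclusion assumes that the SAP's schedule is the one in force. The SAP does not show whether a different delirium time point or a different 6-month outcome was intended, so the error in section 7 is established but the authors' intention is not.

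**What to change.** Before outcome data by arm are examined, amend section 7 as follows:

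1. Name one delirium time point at which CAM is scheduled. One month is the natural choice: it is the last CAM visit and is already modelled in section 5.1, item 2. Naming a single time point matters, because leaving a choice between it and the repeated-measures model would keep the discretion that the amendment is meant to remove. If a 6-month outcome was intended, formally withdraw the analysis and record that in section 11.
2. State that the subgroup is defined by baseline MoCA.
3. State the direction of MoCA positive, and align it with the coding in section 2.1.2, item 4, or reverse that coding so that 1 means impaired.
4. As a clarification only, list arm and cognitive impairment as main effects beside their interaction, with gender, known cognitive decline, baseline delirium and centre kept as they are.
5. Keep the exploratory label.

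The cost is SAP wording and a version entry. No new data collection is needed, because CAM at 1 month and MoCA at baseline are already scheduled.

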8 ADDITIONAL EXPLORATORY ANALYSIS

The following analysis has been planned as exploratory only.

1) Charlson Comorbidity index

The Charlson index [6] assesses whether a patient will live long enough to benefit from a specific screening measure or medical intervention. The Charlson index is used to derive a variable for Charlson score and Charlson probability, and is assessed by baseline and 6 months follow-up. The Charlson index is a 16 item questionnaire (variables *ccicon1 – ccicon16*) with questions on if the patient has a particular comorbidity or not. To obtain the Charlson Comorbidity Index score add up the score from each question in the index, add an extra point if the patient is aged between 50 and 59, add 2 extra points if the patient is aged between 60 and 69, add 3 extra points if the patient is aged between 70 and 79, add 4 extra points if the patient is 80+, and add 0 extra points if the patient is less than 50. To obtain Charlson probability (10-year survival):

$$\text{Charlson probability} = 0.983^{CII*0.9}$$

Where CII = Charlson Comorbidity Index score.

The mean, standard deviation, median, minimum value, and maximum value of the Charlson comorbidity score and Charlson probability will be presented at each time point and in each randomised group. No statistical tests for differences will be performed.

2) Clinical Diagnosis of Delirium at Baseline

Delirium is measured at baseline, 3 days, 5 days, and 1 month follow-up using the CAM questionnaire. A clinical diagnosis of delirium is also collected at baseline. The frequencies and percentages of patients that have a clinical diagnosis of delirium at baseline will be summarised in a two-way table against the frequencies and percentage of patients that were tested positive for delirium by the CAM questionnaire. This is exploratory only to see how these two methods compare. No formal analysis will be conducted.

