2.2 TARGET POPULATION

Inclusion Criteria

- Participant is willing and able to give informed consent for the participation in the study.
- If the participant lacks capacity to consent they have a relative or friend who is a 'personal consultee' or Independent Mental Capacity Advocate who will be invited to advise on whether they believe that participation in the study would be in accordance with the values and interests of the individual.
- Male or Female, aged ≥ 65 years.
- Patient had been referred to the admission avoidance HAH service with CGA and would otherwise require hospital admission for an acute medical event. This will include patients presenting with delirium, functional decline, dependence, falls, immobility or a background of dementia presenting with physical disease.
- In the Investigator's opinion, is able and willing to comply with all trial requirements.
- Willing to allow his or her General Practitioner and consultant, if appropriate, to be notified of participation in the trial.
- English speaking.

The presence of a carer will not be a requirement for enrolment and will depend on the individual circumstances of the patient; this will be at the discretion of the clinician responsible for the patient, as is current clinical practice in each centre.

Exclusion Criteria

- Patients with acute coronary syndrome, this includes myocardial infarction and unstable angina and is characterised by cardiac chest pain and is associated with ECG changes.
- Patients presenting with symptoms which require an acute surgical assessment.
- Patients with a suspected stroke.
- Patients who are receiving end of life care as part of a palliative care pathway.
- Patients who refuse HAH service.
- Patients considered by the clinical staff to be too high risk for home based care, for example those who are physiologically unstable, who are at risk to themselves or if the carer reports HAH care who not be acceptable (in keeping with existing clinical practices for HAH).
- Patients living in a residential setting.

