2.3 SAMPLE SIZE

The sample size is calculated for the primary outcome: living at home at 6 months follow up (the inverse of death or living in a residential care setting), for a 2:1 randomisation ratio with 2/3rd randomized to admission avoidance HAH with CGA and 1/3 to inpatient CGA. Several sources informed our estimate of effect size; these were one of the trials included in the IPD meta-analysis of HAH which recruited frail older people who required hospital level care (similar to the study population we plan to recruit), an audit of 750 patients who received HAH + CGA in Lanarkshire, the RCTs of CGA included in the Cochrane Review and the pooled estimate for the relative effect at 6 months obtained from the IPD Cochrane Review of HAH (3 trials, 607 participants) which was an adjusted Hazard Risk of 0.62 (95% CI 0.45 to 0.87) for mortality. Our proposed study effect estimate is based on a control group (CGA hospital) event rate at 12 months of 50% with a 10% reduction in living in a residential setting to 40% in the CGA at home group, equal to a relative risk of 0.8 which lies towards the top end of the 95% CI for the pooled estimate. We have calculated that a sample size of 1050 to achieve around 83% power at a significance level of 0.05 to detect a 10% absolute difference, assuming a control group event rate at 12 months of 50% and 6% attrition.

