Appendix III. Questionnaire scoring

Questionnaire	Possible range of scores	Higher or lower score indicates better health
Charlson Index (Comorbidity)	0-36	Lower
Barthel Index (Activities of daily living)	0-20	Higher
MOCA (Cognitive impairment)	0-30	Higher ≥26 is considered normal (≥18 is considered normal if visually impaired)
IQCODE short (background cognitive status)	1-5 (mean score across all questions)	Lower (3 indicates not much change in last 10 years)
EQ5D VAS (Health status)	0-100	Higher

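### As printed, the Charlson 10-year survival formula barely responds to the score and gives implausibly high survival for frail older patients; the exponent needs checking before use

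*SAP*

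**What the plan says.** Section 8 of the SAP (Additional exploratory analysis, item 1) derives two variables from the Charlson index at baseline and 6 months: a score and a probability. The score sums the comorbidity items and adds points for age. In this trial the relevant age rules run from "add 2 extra points if the patient is aged between 60 and 69" to "add 4 extra points if the patient is 80" or over. The second variable is introduced with "To obtain Charlson probability (10-year survival" and set equal to 0.983^(0.9 × CII), followed by the definition "Where CII = Charlson Comorbidity Index score".

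The same item says that the index judges whether a patient will survive long enough for a screening measure or treatment to be of benefit. The mean, SD, median, minimum and maximum of both score and probability are to be shown by arm and time point, without tests.

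Three other places bear on the point. Appendix III lists "Charlson Index (Comorbidity) 0-36" as the possible range. Section 2.2 sets entry at "Male or Female, aged ≥ 65 years". Section 2.3 plans the sample size "assuming a control group event rate at 12 months of 50% and 6% attrition".

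**The concern.** A 10-year survival estimate for patients aged 65 or over, frail, with some disability and acutely ill should vary widely with comorbidity and age, and should often be low. The printed expression does neither. It starts near 1 and falls very slowly, so almost any score a participant could have gives a high value.

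A programmer who follows the SAP would produce a table that shows this cohort, in both arms and at both time points, as very likely to be alive in 10 years. The error might not be caught later. The minimum set of analyses for independent validation in section 10 covers the primary, sensitivity and safety analyses and living at home at 12 months, but not this derivation.

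**Working it through.** The SAP states no numerical Charlson probability, so there is no figure to reproduce. The check evaluates the printed rule over the scores that can occur.

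**Inputs.** Formula: 0.983^(0.9 × score) (section 8, item 1). Lowest possible score: 2, because the minimum age is 65 (section 2.2) and ages 60 to 69 carry 2 points (section 8). Score at age 80 or over with no comorbidity: 4 (section 8). Top of the range: 36 (Appendix III).

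**Step 1: response per point.** One extra point multiplies the result by 0.983^0.9 = 0.985, a relative fall of about 1.5%.

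**Step 2: values over the range.**

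| Score | Exponent (0.9 × score) | Printed 10-year survival |
|---|---|---|
| 2 | 1.8 | 97.0% |
| 4 | 3.6 | 94.0% |
| 6 | 5.4 | 91.2% |
| 8 | 7.2 | 88.4% |
| 10 | 9.0 | 85.7% |
| 20 | 18.0 | 73.5% |
| 36 | 32.4 | 57.4% |
| 40 (36 plus 4 age points) | 36.0 | 53.9% |

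The last row is there because the SAP does not say whether the 0 to 36 range already includes age points. To reach 50%, the score would have to be ln(0.5) / (0.9 × ln 0.983) = 44.9, which is outside the range on either reading.

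**Step 3: other groupings of the same symbols.** At score 36, (0.983^score)^0.9 gives 57.4%, 0.983^(score^0.9) gives 65.0%, and 0.9 × 0.983^score gives about 49%. At score 4 they give 94.0%, 94.2% and 84.0%. No regrouping makes the result respond much more steeply to the score.

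**Step 4: comparison with the planned event rate.** Survival at 10 years cannot exceed survival at one year in the same group. Section 2.3 assumes 12-month event rates of 50% (control) and 40% (intervention), but the event is death or residential care, and deaths are not given separately. The table below therefore assumes a range for 12-month mortality m. It shows the score at which the printed 10-year survival equals 1 − m, that is ln(1 − m) / (0.9 × ln 0.983). Below that score, the printed 10-year figure is higher than the assumed one-year survival.

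| Assumed 12-month mortality | Score at which the two are equal |
|---|---|
| 10% | 6.8 |
| 20% | 14.5 |
| 30% | 23.1 |
| 40% | 33.1 |

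This sets a patient-level formula against an assumed cohort average, so it is a plausibility check and not a proof.

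**The case against.** **The text may have lost a symbol.** The formula is displayed mathematics read from a PDF, and a small or nested exponent could have dropped out. This cannot be excluded. The expression is complete and programmable as it stands, however, so checking the source file is the right first step.

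**The 12-month rate is not mortality.** A reader might infer that the SAP contradicts itself by planning for 40 to 50% events at 12 months while giving about 90% survival at 10 years. The documents do not support that. The event is a composite, and a patient who moves into residential care is still alive. With an assumed 12-month mortality of 10%, the printed value is already below one-year survival from a score of about 7. The composite rate supports the point only indirectly.

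**The right formula is not in the documents.** A reader might also infer that one particular term, such as an exponential, is missing, and work out how far the printed values are from the truth. The SAP contains no other form of the rule, and reference [6] is not at hand, so no such gap can be stated. Nor can a value be given for a typical participant, because the SAP gives no distribution of scores.

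**57% is not a firm floor.** It assumes that the range of 36 includes age points. If not, the lowest value is about 54%. The conclusion is unchanged.

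**The stakes are low.** This stands in full. The probability enters no model, subgroup, imputation or safety analysis described in the SAP. The Charlson score is reported beside it and is unaffected. The same formula would apply to both arms, so no treatment effect estimate could change.

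**Conclusion.** The point holds as a minor one. The printed rule does not work as a 10-year survival estimate for this population: it falls by about 1.5% per point, gives 94% to a patient aged 80 or over with no comorbidity, and stays above 50% across the whole stated range. That also defeats the purpose that section 8 gives for the index, since the rule never makes death within 10 years more likely than not.

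The arithmetic rests only on figures in the SAP. The judgement that the values are implausible rests on the described population (aged 65 or over, frail, with a level of disability, and otherwise needing admission for an acute medical event), with the composite event rate as indirect support. The conclusion depends on the formula in the source file being the same as the one read here. What is affected is one set of exploratory, descriptive summaries by arm and time point; the primary result is not touched.

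**What to change.** Before the variable is programmed, check the typeset exponent in the SAP source file and compare it with reference [6]. If the formula is as printed here and differs from the reference, correct it in section 8 and record the change. If it cannot be verified, drop the derived probability and report only the Charlson score. It would also help to state in Appendix III whether the 0 to 36 range includes age points.

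The cost is one formula check and, if needed, one corrected line; no data collection changes. If the source file already has the right exponent, only the program needs checking against it. If the probability is dropped, little is lost, because the score is reported anyway.
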